11.4. HCT Comorbidities Assessment

HCT comorbidities present at baseline will be scored using the HCT comorbidity index assessment (Sorrer 2005) (see Appendix 6 for scoring table).

11.5. PELOD Score

Each subject's PELOD score will be captured at baseline and as a maximum (aggregate) score over the 16-week treatment period; see Appendix 7 for scoring table. For each organ system, the maximum (i.e., worst-case) score over the 16-week treatment period will be used to calculate an aggregate score for the subject.

11.6. Daily Diarrhea Symptoms Assessment

Subjects or their caregivers will use an e-diary to record daily diarrhea symptoms, capturing the number and consistency of stools based on the Bristol Stool Form Scale (see Appendix 8). The e-diary will be reviewed with the subject and caregiver at each visit.

11.7. Concomitant Medications

All medications taken by subjects will be assessed and recorded in the eCRF at each study visit through Week 16, as described in Section 8.6.

11.8. Laboratory Assessments

The minimum test parameters to be evaluated are presented in Table 11.

11.8.1. Hematology and Serum Biochemistry

Blood for hematology, coagulation panel, and serum biochemistry testing will be collected as part of the screening evaluation, prior to randomization on Day 1 (baseline), and at each study visit.

Lymphocyte subset (percent and total [absolute] CD4+ and CD8+ counts) will be performed prior to randomization on Day 1 (baseline) and at each study visit. Other potential immunologic predictors of virologic response (e.g., AdV-specific CTLs) may be analyzed.

Estimated GFR will be calculated and reported by the central safety laboratory based on serum creatinine results.

11.8.2. Urinalysis

Samples for standard urinalysis will be collected as part of the screening evaluation, prior to randomization on Day 1 (baseline), and at Weeks 4, 8, 12, and 16.

Table 11: Study CMX001-999: Clinical Laboratory Evaluations

BIOCHEMISTRY PANEL Alanine aminotransferase (ALT [SGPT]) Albumin Alkaline phosphatase Aspartate aminotransferase (AST [SGOT]) Bilirubin (total and direct [conjugated]) Blood urea nitrogen (BUN) Calcium Creatine phosphokinase (CPK) Creatinine Electrolyte Panel (Na⁺, K⁺, Cl⁻, and HCO₃⁻ [or CO₂]) Gamma-glutamyltransferase (GGT) Globulin, total Glucose Lactate dehydrogenase (LDH) Lipase Phosphate Protein (total) Uric acid
 
URINALYSIS PANEL Albumin (microalbumin) Blood* Glucose Leukocytes (leukocyte esterase)* Protein *Reflex to microscopic analysis if blood or leukocytes are present
	
HAEMATOLOGY PANEL Hematocrit Hemoglobin Mean cell hemoglobin (MCH) Mean cell hemoglobin concentration (MCHC) Mean cell volume (MCV) Platelet count (PLT) Red blood count (RBC) RBC morphology (reticulocytes, schistocytes, etc.) White blood count (WBC) with differential (percent and absolute) Lymphocyte subset (percent and total [absolute] CD4⁺ and CD8⁺)
 
MISCELLANEOUS TESTS Prothrombin time-international normalized ratio (PT-INR) Pregnancy Test HBV DNA, HCV RNA, HIV RNA^a Samples for exploratory biomarker analysis for BCV-related toxicity (e.g., citrulline, ST2, TIM3, and CRP) Immunologic predictors of virologic response (e.g., AdV-specific CTLs)

--	--

^a If documented results within 6 months prior to Day 1 are not available

11.8.3. Pregnancy Screen

Urine screens for pregnancy in female subjects of childbearing potential will be performed as part of the screening evaluation, prior to randomization on Day 1 (baseline), and at Weeks 4, 8, 12, and 16 (or as required by standard site practice). The central safety laboratory will provide urine pregnancy test kits for use at each site, although, if preferred, the site may use testing protocols specified by standard site practice.

11.8.4. Biomarker Analysis

Blood will be collected for exploratory biomarker analysis (e.g., citrulline, ST2, TIM3, and CRP) prior to randomization on Day 1 (baseline) and at each study visit through Week 16. Samples will be stored for future analyses.

11.9. Adverse and Serious Adverse Events

11.9.1. Definition of Adverse Event

An AE is any untoward medical occurrence in a clinical investigation subject, temporally associated with the use of a medicinal product, whether or not considered related to the medicinal product. An AE can therefore be any unfavorable and unintended sign (including an abnormal laboratory finding, for example), symptom, or disease (new or exacerbated), temporally associated with the use of a medicinal product, whether or not considered related to the medicinal product.

AEs will be recorded from the time of administration of the first dose of BCV or, for subjects randomized to SoC, from the date of randomization, until the subject has completed the Week 16 assessment or premature discontinuation from the study. In addition, any study procedure-related AE that occurs after study participants have signed the informed consent form (ICF) and prior to administration of the first dose of BCV (or randomization to SoC) will be recorded as an AE for the purposes of this protocol. After the Week 16 assessment, and until completion of the Week 36 assessment, only SAEs, regardless of treatment arm or relatedness, will be recorded and reported to Chimerix Safety (or designee).

Disease-specific signs and symptoms (including clinical laboratory abnormalities) that were ongoing before administration of the first dose of BCV (or randomization to SoC) should not be considered AEs unless they worsen (i.e., increase in frequency or severity by at least one CTCAE grade) after administration of the first BCV dose (or randomization to SoC). In addition, unless fatal, AEs related to AdV infection (including viremia or viral load in other body fluids/compartments) or AdV disease do not need to be reported as AEs or SAEs for the purposes of this study; these events will be captured as part of the endpoints for the study.

In addition, the following will NOT be considered AEs for the purposes of this study:

1. Medical or surgical procedures (e.g., surgery, endoscopy, transfusion); the condition that requires the procedure is the AE
2. Situations where an untoward medical occurrence had not occurred (e.g., hospitalization for elective surgery or social and/or convenience admissions)
3. Overdose of BCV or concomitant medication without any signs or symptoms, unless the subject was hospitalized for observation
4. Uncomplicated pregnancy
5. An induced elective abortion to terminate a pregnancy without medical reason

Subjects experiencing clinically significant AEs must be monitored periodically until symptoms subside or until there is a satisfactory explanation for the AE, whichever is later. Additionally, clinically significant abnormal laboratory values should be monitored periodically using central

laboratory results until the abnormality resolves, returns to baseline levels, or is otherwise explained.

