7.3. Subject Withdrawal Criteria

Subjects randomized to receive BCV must be managed according to the toxicity management criteria described in Section 8.3.2. Subjects randomized to the SoC arm will be managed according to local or institutional practice guidelines and any relevant product labelling.

Subjects randomized to BCV who experience any of the following criteria after initiating treatment in this study will be required to discontinue BCV, but will continue to be followed in the study:

- Subject request to discontinue for any reason
- TEAE that necessitates the discontinuation of BCV as described in Section 8.3.2
- If the investigator or the subject's primary care provider believes that participation in the study is no longer in the best interests of the subject
- Pregnancy in a female subject

Female subjects who become pregnant will be immediately discontinued from BCV, but will continue to be followed in the study. See Section 11.9.5 for actions to take and reporting requirements for pregnancy. Pregnancies in female subjects randomized to the SoC arm must be reported according to local guidelines and relevant product labelling.

- Discontinuation of the study at the request of Chimerix, a regulatory agency, or the governing institutional review board, research ethics board, or independent ethics committee (collectively referred to as "ethics committee" [EC])

In addition, if any of the following criteria are met, BCV will be discontinued at the discretion of the investigator, in consultation with the Chimerix Medical Monitor (or designee):

- Development of an exclusionary condition, including a decrease in eGFR to < 15 mL/min considered related to BCV, or unrelated to BCV but not being dialyzed; see Section 8.3.2.6
- Treatment with, or requirement for treatment with, a prohibited or excluded medication; see Section 8.6.1.1
- Subject is not compliant with the protocol (i.e., significant protocol deviation)

All subjects who are randomized will be followed in the study through completion of the Week 36 assessment, including subjects who discontinue BCV for any reason and subjects who are randomized but not dosed in either arm. The subjects will be managed at the discretion of the responsible investigator according to local SoC, but will continue to be monitored in accordance with the Schedule of Study Assessments/Procedures (see Section 6.2).

Subjects who are randomized and who do not complete the study will not be replaced.

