8.2. BCV Administration

Subjects randomized to the BCV treatment arm will receive BCV administered orally as 10 mg/mL suspension.

Subjects will receive a BCV dosage regimen based on their lowest body weight within 30 days prior to Day 1 (to best represent dry weight) and their concurrent cyclosporine use (Table 6).

Table 6: BCV Dosage Regimens for Study CMX001-999

	Initial BCV Dose Regimen	Consolidated BCV Dose Regimen
Cyclosporine	1.4 mg/kg (up to maximum 70 mg) BIW	2.8 mg/kg (up to maximum 140 mg) QW
No cyclosporine	2 mg/kg (up to maximum 100 mg) BIW	4 mg/kg (up to maximum 200 mg) QW

Note: Dosing weight = lowest body weight (in kilograms) within 30 days prior to Day 1.

Abbreviations: BIW = twice weekly; QW = once weekly

As described in Section 8.6, co-administration of BCV and cyclosporine has been shown to increase plasma BCV exposure. Therefore, subjects taking cyclosporine on Day 1 or who initiate cyclosporine at any time while taking BCV will receive a modified dose of BCV of 1.4 mg/kg, up to a maximum of 70 mg, BIW. Subjects who discontinue cyclosporine while taking BCV should increase the BCV dose to 2 mg/kg, up to a maximum of 100 mg, starting with the next scheduled BCV dose following the discontinuation of cyclosporine.

Each BCV dose should be administered using an oral dosing syringe. A 5-mL dosing syringe is recommended for BCV doses \leq 50 mg, and a 10-mL dosing syringe is recommended for BCV doses $>$ 50 mg. [Note: The study drug kits DO NOT include oral dosing syringes.]

Referring to Section 8.3.2, subjects who resume BCV therapy after a mandated interruption due to a TEAE will resume therapy at a consolidated QW dose of 4 mg/kg (up to a maximum of 200 mg) QW for subjects not receiving concurrent cyclosporine, or 2.8 mg/kg (up to a maximum of 140 mg) QW for subjects receiving concurrent cyclosporine (Table 6).

The dose (volume of BCV oral suspension to be administered) should be determined using the dosing tables provided in Appendix 2 (see Table 14 for BCV dosing of subjects receiving concurrent cyclosporine and Table 15 for BCV dosing of subjects not receiving concurrent cyclosporine).

See Section 9 for detailed description of appropriate storage and management of BCV.

Whenever possible, the BCV doses should be given with food (with or within 30 minutes of finishing a meal) to potentially improve tolerability.

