For subjects with CTCAE Grade 1 diarrhea or no diarrhea at baseline, BCV must be interrupted for treatment-emergent CTCAE Grade 2 or higher diarrhea. This includes new-onset Grade 2 or higher diarrhea or progression from Grade 1 to Grade 2 or higher diarrhea, regardless of the cause of the diarrhea.

In general, changing multiple therapies at the same time (e.g., interrupting BCV and starting steroids for new-onset or worsening GI GVHD) is not recommended. In order to assess response to BCV treatment interruption, start of (or increase in) steroid therapy for new-onset or worsening GI GVHD should be delayed, when possible.

- If diarrhea does not improve following ≥ 7 days interruption (at least 6 calendar days off BCV), a trial of steroid therapy for new-onset or worsening GI GVHD (while BCV is still being held) may be considered if deemed clinically appropriate.

If diarrhea does not improve to \leq CTCAE Grade 1 during interruption, BCV must not be resumed.

If diarrhea improves to \leq CTCAE Grade 1 in intensity, subjects may resume dosing of BCV, but no sooner than 7 days (i.e., at least 6 full days off drug) following the last BCV dose administration.

- If resumed, BCV must be administered in a consolidated QW dose (total weekly dose administered once weekly, i.e., 4 mg/kg, up to a maximum of 200 mg, QW in the absence of concurrent cyclosporine, or 2.8 mg/kg, up to a maximum of 140 mg, QW for subjects taking concurrent cyclosporine) to potentially improve tolerability, as weekly dosing intervals allow more time for GI mucosal regeneration between doses.

Treatment with the consolidated QW BCV dose will be continued through Week 16 post-randomization or until confirmed undetectable AdV viremia in plasma, whichever occurs first.

Recurrence of CTCAE Grade 2 or higher diarrhea after restarting BCV requires permanent discontinuation of BCV.

8.3.2.3. Treatment-emergent Diarrhea AEs in Subjects with Grade 2 or 3 Diarrhea Attributed to AdV at Baseline

For subjects with CTCAE Grade 2 or 3 diarrhea at baseline that is attributed to AdV, BCV dosing must be interrupted if:

- the diarrhea has not improved to \leq CTCAE Grade 1 after 21 days of therapy, or

- the subject experiences on-treatment worsening of one CTCAE grade or more at any time following initiation of BCV (i.e., Grade 2 worsens to \geq Grade 3, or Grade 3 worsens to \geq Grade 4), regardless of the cause of the diarrhea

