Grade 2: Increase of 4 to 6 stools per day over baseline; or moderate increase in ostomy output compared to baseline

Grade 3: Increase of \geq 7 stools per day over baseline; incontinence; hospitalization indicated; or severe increase in ostomy output compared to baseline; limiting self-care activities of daily living (ADLs)

Grade 4: Life-threatening consequences; urgent intervention indicated

Note: Action taken with BCV is regardless of the etiology of diarrhea.

Note: Pre-transplant stool output (= baseline).

Table 9: Recommended Management/Evaluation of Treatment-emergent GI Adverse Events during BCV Therapy

	Grade 1 Events	Grade 2 or Higher Events
Action with BCV	See Table 8 and Section 8.3.2	
Other interventions	
 • Avoid food/drinks that affect water transport (e.g., caffeine, alcohol, carminative spices, concentrated sugar syrups) • Avoid lactose- and sucrose-containing products • Adjust other medications associated with GI effects (e.g., macrolides, magnesium, MMF) • Symptomatic treatment dosed as needed (e.g., anti-emetics, anti-diarrheals) • Avoid starting steroid/immunosuppressants for GVHD (while dosing BCV) unless Grade 1 diarrhea persists for > 14 days 	
 • Same as for Grade 1 events • Interrupt other medications that may cause GI events (e.g., magnesium supplements, MMF) • Measure levels of immunosuppressants • Consider symptomatic treatment (e.g., anti-emetics, anti-diarrheals) dosed at regular intervals, if clinically appropriate • Fluid supplementation to maintain hydration
Other diagnostic evaluations	
 • Monitor hydration status, and supplement as needed • Evaluate for other infection • Evaluate for acute GVHD in other organ systems; consider non-GI biopsy 	
 • Same as for Grade 1 events

NOTE: When considering new-onset or worsening GI GVHD as the cause of GI symptoms:

- **Co-administration of BCV and steroids for GI GVHD is not recommended**
- In order to assess response to BCV treatment interruption, start of (or increase in) **steroid therapy for GI GVHD should be delayed, when possible**

If diarrhea does not improve following ≥ 7 days interruption (i.e., at least 6 full days off BCV), a trial of steroid therapy for new or worsening GI GVHD (while BCV is still being held) may be considered, if deemed clinically appropriate.

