11.9.2. Definition of Serious Adverse Event

An SAE is any AE that results in any of the following outcomes:

- Death
- Life-threatening (subject at immediate risk of death)
- Requires inpatient hospitalization or prolongation of existing hospitalization
- Results in congenital anomaly/birth defect
- Results in a persistent or significant disability or incapacity

Important medical events that may not result in death, be life-threatening, or require/prolong hospitalization may be considered an SAE when, based upon appropriate medical judgment, they may jeopardize the subject and may require medical or surgical intervention to prevent one of the outcomes listed in this definition. Unless fatal, SAEs related to AdV infection or AdV disease do not need to be reported as SAEs for the purposes of this study; these events will be captured as part of the endpoints for the study.

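### Treatment-emergent AE windows differ by arm, and open-label attribution to AdV can keep worsening diarrhea out of the AE counts

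*Combined protocol and SAP*

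**What the plan says.** **Windows.** Section 5.3.3 lists TEAE incidence first among the safety endpoints. Section 12.6.1 defines TEAEs separately by arm:

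- BCV: from first dose to 7 days after the last dose.
- SoC with anti-AdV therapy: from Day 1 to 7 days after the last dose of that therapy.
- SoC without anti-AdV therapy: from Day 1 to Week 16.

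Follow-up AEs are defined only by the last dose of study drug. The same section also plans on-study tables (all AEs, Grade 3+, SAEs) from Day 1 to Week 16 in both arms.

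**Recording.** Section 11.9.1 first says that ongoing disease-specific signs "should not be considered AEs unless they worsen (i.e., increase in frequency or severity by at least one CTCAE grade". It then adds that non-fatal AEs related to AdV infection "or AdV disease do not need to be reported as AEs or SAEs for the purposes of this study", on the ground that the study endpoints will capture them. Section 11.9.2 repeats this for serious events: "Unless fatal, SAEs related to AdV infection or AdV disease do not need to be reported as SAEs for the purposes of this study".

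Section 8.3.2.3, headed "Treatment-emergent Diarrhea AEs in Subjects with Grade 2 or 3 Diarrhea Attributed to AdV at Baseline", requires BCV interruption if "the subject experiences on-treatment worsening of one CTCAE grade or more at any time following initiation of BCV". The note to Table 8 says "Action taken with BCV is regardless of the etiology of diarrhea". Sections 8.2 and 7.3 use AE language for these events: "subjects who resume BCV therapy after a mandated interruption due to a TEAE" and "TEAE that necessitates the discontinuation of BCV as described in Section 8.3.2".

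**The concern.** Comparing safety and tolerability is part of the primary objective (Section 5.1), and diarrhea is BCV's leading toxicity. Two features of the plan weaken that comparison.

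First, the leading safety endpoint counts events over periods whose length depends on arm and treatment. BCV stops at confirmed clearance, so a drug that clears virus quickly has a short window. An untreated SoC subject is counted for the full 16 weeks. A reader of the TEAE table could mistake window length for tolerability.

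Second, the dosing action for diarrhea ignores its cause, but the duty to report it depends on cause. Treatment is open-label (Section 8.8), and Section 4.3.7 says that even histopathology cannot separate gut injury due to AdV, GVHD and BCV. An event serious enough to stop dosing may thus go unrecorded as an AE. Missing events would affect the counts of AEs leading to interruption, Grade 3+ AEs and SAEs in Sections 5.3.3 and 12.6.1, and the matching items in the DSMB package (Section 4.5.1).

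**Working it through.** The plan states no figure to reproduce here. The calculation only gives the scale of the window difference.

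**Inputs**

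- Median time to undetectable viremia on BCV: 12 to 22 days in pediatric subjects of CMX001-304 (Section 4.3.3.2), or 4 weeks in the cohort report in Section 4.4.
- Median time to clearance on IV CDV: 9 weeks (Section 4.4).
- Confirmatory sample: 7 to 14 days after the first undetectable result (Section 8.3.1).
- Tail after last dose: 7 days (Section 12.6.1).
- Event rate: assumed constant and equal in all groups, at 0.005, 0.01 or 0.02 per day.

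**Window length** = days to undetectable + days to confirmation + 7, assuming treatment stops at confirmation and is not restarted.

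- BCV, Section 4.3.3.2 median: 12 + 7 + 7 = 26 to 22 + 14 + 7 = 43 days.
- BCV, Section 4.4 median: 28 + 7 + 7 = 42 to 28 + 14 + 7 = 49 days.
- SoC on CDV: 63 + 7 = 70 days if CDV stops at clearance. With the same confirmation lag as BCV: 63 + 7 + 7 = 77 to 63 + 14 + 7 = 84 days.
- SoC untreated: 16 x 7 = 112 days.

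**Crude incidence** = 1 - exp(-rate x days), with no true difference between groups:

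| Rate/day | BCV 26-43 d | BCV 42-49 d | CDV 70 d | Untreated 112 d |
|---|---|---|---|---|
| 0.005 | 12-19% | 19-22% | 30% | 43% |
| 0.01 | 23-35% | 34-39% | 50% | 67% |
| 0.02 | 41-58% | 57-62% | 75% | 89% |

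With the confirmation lag added, the CDV figure at 0.01 per day is 54-57%.

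Individual windows overlap. The ranges in Section 4.4 (BCV 2 to 9 weeks, CDV 3 to 15 weeks) give 14 + 7 + 7 = 28 to 63 + 14 + 7 = 84 days for BCV, and 21 + 7 = 28 to 105 + 7 = 112 days for CDV.

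**Tracing one event through the text.** A BCV subject has AdV-attributed Grade 2 diarrhea at Day 1, which worsens to Grade 3.

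1. Section 8.3.2.3 requires interruption whatever the cause.
2. The worsening rule in Section 11.9.1 makes it an AE.
3. The next sentence of Section 11.9.1 removes the duty to report it if the investigator relates it to AdV.
4. Section 11.9.3 requires an AE entry because of interruption only for laboratory abnormalities.
5. The stated fallback is capture as an endpoint. In Section 5.3.2, disease progression covers only subjects asymptomatic at baseline, and the resolution endpoint does not count worsening.

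The event can therefore be neither a required AE nor a progression endpoint. For a subject asymptomatic at baseline, probable GI AdV disease in Appendix 5 lists endoscopic evidence among its criteria (the grouping of alternatives is ambiguous), so new diarrhea without endoscopy may not qualify either.

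**The case against.** **Recording.** A reader might infer that the exemption flatly contradicts Sections 7.3, 8.2 and 8.3.2. It does not. It is a permissive reporting carve-out, and those sections use AE language to trigger dosing actions without telling sites what to record. The heading of 8.3.2.3 attributes the baseline diarrhea to AdV, not the later event. The two sentences in 11.9.1 can be read as a general rule followed by a specific exclusion. Diarrhea judged due to BCV, GVHD or another cause stays reportable.

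Other data help. Daily diarrhea symptoms are kept in the e-diary in both arms (Section 8.7.1), AdV symptoms are entered at each visit (10.2), and BCV dosing dates are captured (8.2.1). The Grade 2+ diarrhea endpoint in 5.3.3 is not worded as an AE endpoint, and its source may be settled in the SAP details to which Section 12 defers. The DSMB list is a minimum. All of this stands and narrows the point, but none of it puts the traced event into the interruption, Grade 3+ or SAE counts.

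**Windows.** Safety is generally descriptive (Section 12.6), and Section 12.6.1 makes on-study AEs the default for summaries. Nothing names the TEAE tables as the main comparison. That also stands, so the remedy is mostly a choice among tables already planned. Even so, TEAE incidence is the first listed endpoint, and the plan does not warn against comparing it across arms.

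**Size.** The Section 4.4 medians come from small groups (18 on BCV, 23 on CDV). A constant rate does not fit diarrhea, whose typical pediatric onset is given as 4 to 6 weeks (Section 4.3.1). The share of untreated SoC subjects is unknown. The percentages are therefore illustrations only.

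**Conclusion.** Both parts hold in limited form, and both should be fixed.

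On windows, crude TEAE incidence is not a like-for-like comparison. At an assumed 0.01 per day it would be about 23-35% or 34-39% on BCV, depending on which clearance median is used, against 67% in untreated SoC, with no true difference. This assumes a constant equal rate, stopping at confirmed clearance and no restart. A reader might infer that every BCV window is shorter or that all the AE tables are distorted. The individual ranges overlap, and the on-study tables already share one window. The different start of AE recording matters little, because the first BCV dose must follow randomization within 24 hours. Follow-up AEs have no definition for the SoC arm.

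On recording, AdV-attributed worsening of diarrhea that forces interruption can be missing from counts meant to show tolerability, and the endpoint fallback does not cover it. A reader might infer a bias in favor of BCV. The documents do not support that: the exemption applies to both arms, and neither the direction nor the size can be estimated. The primary efficacy analysis is not affected.

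**What to change.** **Analysis.** In Sections 5.3.3 and 12.6.1, name the planned on-study summaries (Day 1 to Week 16, both arms) as the between-arm safety comparison. Keep the TEAE tables as within-arm description, or add exposure-adjusted rates. Define follow-up AEs for SoC or present them for BCV only. This costs a few sentences and, if rates are added, some programming.

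**Recording only.** Reconcile Sections 11.9.1 and 11.9.2 with Section 8.3.2. State that, in both arms and regardless of attribution to AdV, Grade 2+ diarrhea that is new or at least one CTCAE grade worse than at Day 1 is recorded as an AE, and as an SAE if serious. This uses the worsening step already in 11.9.1.

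Interruption itself should not be the recording trigger. Mandated interruption exists only for BCV (SoC follows local practice, Section 8.1), so such a trigger would add entries mainly in that arm. It would also capture unchanged baseline diarrhea interrupted at 21 days, which the worsening rule says is not an AE. Count those interruptions from the dosing records.

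The cost is some extra AE and SAE entries, a number of which will reflect AdV disease. No new assessments are needed, and no change to treatment rules is proposed.
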